The following table outlines the changes made to the protocol and the rationale.

Description of Change	Brief Rationale	Sections Changed
The minimum interval between study drug dose #1 and dose #2 was reduced from 18 weeks to 12 weeks. - Time window for day 85 environmental exposure unit (EEU) challenges expanded from "±7d" to "-28 to +14" days to allow participants with a shorter interval to complete Part A assessments prior to the birch season. Therefore, the day 85 visit can be completed from as early as day 57 and up to day 99. - Minimum interval between EEU challenges clarified at approximately 1 week or longer for all EEU challenges. - Participants who experience a high symptom burden that is assessed as due to tree pollens may not complete the day 57 and/or day 85 EEU challenge(s). Therefore, the primary analysis may be performed after all participants complete at least the day 29, rather than the day 57, EEU	A shorter interval between doses will allow participants to be enrolled over a longer duration within the seasonality constraints to complete both the out-of-season and in-season portions of the study and aid with enrollment timelines. Flexibility to decrease patient burden for visit assessments was added given the reduced timing between some visits that may apply.	Protocol Synopsis: Study Duration; Statistical Plan Section 3.2.2 Rationale for Dose Selection Section 5.1 Study Description and Duration Section 5.2 Planned Analyses Figure 1: Study Flow Diagram Section 8.1.1 Footnotes for the Schedule of Events Table, footnotes #6, #14, #40 and #41 Section 10.5 Timing of Statistical Analysis
 challenges in Part A or discontinue. Visit 10 may not be performed if participants are expected to be dosed within 3 weeks after the prior EEU visit. If visit 10 is not performed, then all visit 10 assessments (without any 		
duplication) should be performed at the last prior EEU visit (including serum pregnancy test, e-diary, dispensing rescue medications, etc)		

Description of Change	Brief Rationale	Sections Changed

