2.2. Secondary Objectives and Endpoints

The secondary objectives and endpoints of the study are outlined below:

Secondary Objectives	Secondary Endpoints
• To assess the magnitude and duration of efficacy of a single dose of the anti-Bet v 1 monoclonal antibodies (dose #1) in the reduction of allergic symptoms during the out-of-season birch allergen EEU challenges in participants receiving REGN5713-5714-5715 versus placebo, REGN5713-5715 versus placebo, and REGN5715 versus placebo (Part A)	 The mean of symptom scores during out-of-season birch allergen EEU challenges at days 29, 57, and 85 TNSS (2 to 6 hours) (except day 29 for 3-mAb) TOSS (2 to 6 hours) TSS (2 to 6 hours) The change and percent change from pre-treatment baseline in symptom scores during out-of-season birch allergen EEU challenges at days 29, 57, and 85 TNSS (2 to 6 hours) TOSS (2 to 6 hours) TOSS (2 to 6 hours) TSS (2 to 6 hours)
• To assess the efficacy of the anti-Bet v 1 monoclonal antibodies (dose #1) in the reduction of skin test reactivity from pre-treatment baseline by inhibiting a wheal response to a titrated skin prick test with birch and related allergens (eg, alder, oak) during out-of-season assessments in participants who receive REGN5713-5714-5715 versus placebo, REGN5713-5715 versus placebo, and REGN5715 versus placebo (Part A)	• The change and percent change from pre-treatment baseline at days 29, 57, 85, and 127 in the birch (and related allergens) titrated SPT mean wheal diameter AUC

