The pharmacokinetics (PK) of REGN5713-5714-5715 are consistent in both clinical studies, exhibiting linear, dose-proportional PK with a half-life of 26.9, 34.0, and 35.1 days for REGN5713, REGN5714, and REGN5715, respectively. Dose #2 in Part B of this study is expected to be administered at least 12 weeks from dose #1 in Part A. The dosing interval in this study is primarily driven by timing of participant enrollment and the pollen season while ensuring accumulation of study drug is within exposure (C_{max} and AUC) observed in the FIH study following 300 mg/mAb IV dosing. With a minimum dosing interval of 12 weeks, accumulation of REGN5713-5714-5715 is expected to be approximately 15% between dose #1 and dose #2 and is predicted to be within the C_{max} and AUC that were measured in the FIH trial following administration of 300 mg/mAb IV, which showed a favorable safety profile. Additionally, analysis of the concentration-response relationship between concentrations of REGN5713-5714-5715 and various clinical endpoints has shown consistent responses across a range of concentrations.

Additional information on clinical and preclinical PK, PD, and safety can be found in the Investigator's Brochure.

Based on the above summary of safety, PK, and PD data, a dose of 300 mg/mAb mg SC is expected to provide efficacy in an EEU setting, as well as in the field setting.

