^[1] Endpoints related to tSPT at day 127 will be analyzed in subgroup that had a visit 10 performed at least 12 weeks after Part A dose (not included if visit 10 combined with other visits or if visit 10 done prior to other out-of-season visits).

^[2] Rescue medication may be given during the EEU challenge if any severe or clinically concerning reactions (as judged by the PI).

^[3] EEU symptom scores include TNSS (2 to 6 hours), TOSS (2 to 6 hours), TSS (2 to 6 hours).

^[4] Field symptom scores from e-diary include CSMS [TSS+DMS], TSS [TNSS+TOSS], daily TNSS, daily TOSS, and DMS.

^[5] If there is no protocol defined BPS due to local climactic conditions at any pollen site, then those data will not be included in the calculation for field data.

^[6] Whether the medication is used due to birch pollen related symptoms (considered treatment failure) or not will be adjudicated in a blinded manner.

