11.4. Assignment of Data to Visit Windows and Unscheduled Assessments

Unscheduled Assessments

Data analyzed by-visit-analysis (including efficacy, laboratory data, vital sign, ADA) will be summarized by the study scheduled visits described in the "Schedule of Events" of study protocol and SAP.

The analysis visit windows are created per study Schedule of Events (SOE) table for each parameter and will be applied if the data from study scheduled visits are unavailable. The following general rules will be applied to unscheduled visit and/or early termination (ET) visit mapping for each parameter.

- 1. If ET visit falls in an analysis window which already has non-missing observed value of this parameter from the scheduled visit, ET will be mapped to the next scheduled visit in the same part.
- 2. If both ET visit and unscheduled visit of the same parameter are available in the same analysis visit window, only ET visit will be mapped.
- 3. If multiple unscheduled visits of the same parameter are available in the same analysis visit window, the unscheduled visits will be mapped using the following rules:
 - a. The closest unscheduled visit from the target day will be selected.
 - b. If the distance is a tie, the unscheduled visit after the target day of the scheduled visit will be used.
 - c. If multiple unscheduled visits exist on the same day, the first unscheduled visit will be used.
- 4. If mapping distance is greater than 6 weeks, the unscheduled visit will not be mapped.

Unscheduled visits and ET visit will be mapped per the following analysis visit windows for Part A and Part B based on the study day/visit of each parameter, respectively.

- 1. Part A visit window: All data collected after the last out-of-season EEU visit and/or the Visit 10 (whichever is later) will not be used for Part A analysis.
- 2. Part B visit window: All data not in Part A visit window will be included in Part B visit window.

Table 4: Analysis Visit Window for Safety and Laboratory Testings

	Visit	Tangat		, Physical nation	Hematology,	Drug	
Part	from SOE	Target Study Day ¹	Allergic to Oak ²	Not Allergic to Oak ²	Blood chemistry	Concentration sample	ADA sample
	Baseline	<=1			<=1		<=1
	Visit 6	29	[2, 33]	[2, 43]	[2, 43]	[2, 43]	-
Part	Visit 7	36	[34, 47]	-	-	-	-
Α	Visit 8	57	[48, 61]	[44, 61]	[44, 61]	[44, 61]	-
	Visit 9	85	>=	62	>=62	>=62	>=2
	Visit 10 ³	Before the dose in Part B	All data aft	er the last ou	t-of-season EEU	visit and before th	e dose in Part B.

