14. APPENDIX

14.1. Summary of Statistical Analyses

Efficacy/PD Analysis:

Endpoint	Analysis Populations	Primary Analysis	Statistical Method	Supportive Analysis	Subgroup Analysis	Other Analyses
Primary E	ndpoint					
EEU TNSS (2- 6 hours)	FAS	Mean at day 29 for 3-mAb versus placebo	ANCOVA model with treatment group and stratification factors as fixed effect and the baseline mean TNSS (2 to 6 hours) at visit 2 as a covariate.	Yes, sensitivity and supplemental analysis described in Section 7.2.1.2	Yes, subgroups are listed in Section 7.2 .1.3	Plots
Secondary	Endpoints					
EEU (2-6 hours): TNSS, TOSS, TSS	FAS	Mean, change and percent change from pre-treatment baseline, at days 29*, 57, 85 for each of anti-bet v 1 monoclonal antibodies versus placebo	Same as above	No	No	Numerical comparison between three anti-bet v 1 monoclonal antibodies.
EEU (2-6 hours): TNSS, TOSS, TSS	FAS with subjects allergic to oak	Mean, change and percent change from pre-treatment baseline, at days 36 for each of anti-bet v 1 monoclonal antibodies versus placebo	Same as above	No	No	Comparison between combined active group versus placebo
EEU (2-6 hours): TNSS, TOSS,	FAS - B	Mean for each of anti-bet v 1 monoclonal antibodies versus placebo	Same as above	No	No	No
CSMS, TSS, TNSS, TOSS, DMS	FAS - B	Mean, change and percent change from pre-treatment and pre-season baseline, in BPS, peak BPS for each of anti-bet v 1 monoclonal antibodies versus placebo	Same as above except for the average pollen count during local BPS will also be used as a covariate in the model.	No	No	Analyses using 30 grains/ m³ as the cutoff for defining BPS start and end

Endpoint	Analysis Populations	Primary Analysis	Statistical Method	Supportive Analysis	Subgroup Analysis	Other Analyses
RQLQ(S)	FAS - B	Mean, change and percent change from pre-treatment and pre-season baseline, in BPS, peak BPS for each of anti-bet v 1 monoclonal antibodies versus placebo	Same as above	No	No	No
Titrated SPT MWD AUC	FAS for Day 29, 57, and 85 FAS with visit 10 performed at least 12 weeks after dose #1 for Day 127	Change and percent change from pretreatment baseline, at days 29, 57, 85 and 127 for each of antibet v 1 monoclonal antibodies versus placebo	Same as above	No	No	Plots; Numerical comparison between three anti-Bet v 1 monoclonal antibodies.

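### The nominal day 85 birch challenge may be done from day 57 and is analyzed without regard to actual day, so the duration-of-efficacy results may partly reflect earlier measurements

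*SAP*

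**What the plan says.** - **Objective.** Protocol 2.2 sets a secondary objective that begins "To assess the magnitude and duration of efficacy of a single dose of the anti-Bet v 1 monoclonal antibodies". Its endpoints are symptom scores in out-of-season birch EEU challenges at days 29, 57 and 85. Protocol 3.2.1 explains that several out-of-season days are tested because the timing of dosing relative to the season, and the season itself, vary.
- **Window.** Protocol Table 1 places visit 8 at day 57 ±7 days and visit 9 at day 85 with a window of -28 to +14 days. The amendment history puts the second window in words, consistent with the current table: "the day 85 visit can be completed from as early as day 57 and up to day 99". It says the change lets participants with a shorter interval finish Part A before the birch season.
- **Labeling.** SAP 11.4 states: "Data analyzed by-visit-analysis (including efficacy, laboratory data, vital sign, ADA) will be summarized by the study scheduled visits described in" the schedule of events. Its actual-day windows (SAP Table 4) are a fallback for when scheduled-visit data are unavailable. They cover vital signs, physical examination, laboratory, drug concentration and ADA data, not EEU scores or skin tests.
- **Durability set.** SAP 3.3 defines CS-A by completion of visits 6, 8 and 9, with no condition on when they took place.
- **Supportive analyses.** SAP 14.1 lists none for the secondary EEU or skin-test endpoints, and no analysis by actual day since dose #1 appears elsewhere.
- **Day 127 skin test.** SAP Table 3, footnote 1: "tSPT at day 127 will be analyzed in subgroup that had a visit 10 performed at least 12 weeks after Part A dose". The footnote also excludes a visit 10 combined with another visit or held before other out-of-season visits. SAP 14.1 repeats the floor: "FAS with visit 10 performed at least 12 weeks after dose #1 for Day 127". Protocol Table 1 shows visit 10 at day 127 ±7, but footnote 13 lets visits 10 to 15 move with the season.

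**The concern.** A challenge done on day 57 and one done on day 99 are both reported as day 85. Early visits are a designed feature of the amended schedule, because the window was extended much further on the early side for people with little time before the season. If many visit 9 challenges fall early, the day 85 estimate drifts toward the day 57 effect. A visit 8 versus visit 9 comparison, in CS-A or in the full analysis set, may then look stable simply because little time passed between the two.

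The phase 1b symptom challenges stopped at day 57 (Protocol Introduction), so day 85 is the new information on how long a symptom effect lasts. Without actual-day information, a reader of the results could not tell a lasting effect from an early measurement.

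**Working it through.** **1. Windows (Protocol Table 1).**
- Visit 8: 57 - 7 = 50 to 57 + 7 = 64.
- Visit 9: 85 - 28 = 57 to 85 + 14 = 99.
- Overlap: day 57 to day 64. With the recommended spacing of about one week between challenges (footnote 6), visit 8 on day 50 and visit 9 on day 57 are both in window.
- Dose #2 may be given 12 weeks after dose #1, which is study day 84 + 1 = 85. Footnote 6 also recommends about one week between a challenge and dosing. A participant dosed at the minimum interval would therefore have visit 9 by about day 85 - 7 = 78.

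**2. Check of the plan's own exposure figure.** Protocol 3.2.2 gives a "half-life of 26.9, 34.0, and 35.1 days for REGN5713, REGN5714, and REGN5715, respectively" and expects about 15% accumulation at a 12-week interval. The fraction remaining after 84 days is 2^(-84/half-life): 11.5%, 18.0% and 19.0%, mean 16.2%. This agrees with the stated figure, so simple exponential decline is adequate here.

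**3. Exposure at the edges of the windows.** Ratio = 2^(gap in days/half-life).

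| Comparison | REGN5713 | REGN5714 | REGN5715 |
|---|---|---|---|
| Day 57 relative to day 85 (28 days) | 2.06 | 1.77 | 1.74 |
| Day 99 relative to day 85 | 0.70 | 0.75 | 0.76 |
| Day 85 relative to day 127 (42 days) | 2.95 | 2.35 | 2.29 |

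**4. Illustration of the possible effect on the day 85 estimate.** Neither the share of early visits nor the true day 85 effect is in the documents; both are assumptions. The phase 1b improvement in TNSS AUC (hour 0 to 1, nasal challenge) was 27% on day 29 and 19% on day 57. A straight line through these falls (27 - 19)/28 = 0.286 points per day, giving 19 - 8 = 11% on day 85. At the other extreme the effect stays at 19%. With a share f tested on day 57 and the rest on day 85, the reported effect is 19f + (true effect)(1 - f).

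| True day 85 effect | f = 0.25 | f = 0.50 | f = 0.75 |
|---|---|---|---|
| 11% | 13% | 15% | 17% |
| 15% | 16% | 17% | 18% |
| 19% (flat) | 19% | 19% | 19% |

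In the first row, on the planning placebo mean of 5.35, the shift is 2%, 4% or 6% of 5.35, that is 0.11, 0.21 or 0.32 TNSS points. The standard error of a difference at the planning SD of 2.8 and 65 per arm is 2.8 × √(2/65) = 0.49, so the shift is about 0.2 to 0.65 standard errors.

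**5. Skin test.** The 12-week floor is study day 85, which is 127 - 85 = 42 days before the nominal day. Phase 1b placebo-adjusted changes in skin-test AUC were -72.39%, -65.61%, -77.90% and -73.56% on days 8, 29, 57 and 113, with no decline over time.

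**The case against.** A reader might infer that the duration objective will be answered with earlier, higher-exposure data and that durability will look better than it is. The documents do not support that much.

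- They give permitted limits, not a distribution. Visit 9 may also be late, to day 99, which pulls the other way. SAP 2.1 says some out-of-season challenges may not be performed for late enrollees, and Protocol footnote 40 lets highly symptomatic participants skip day 57 and/or day 85, so some short-interval participants will be missing rather than early.
- Higher exposure need not mean a larger effect. Protocol 3.2.2 reports consistent responses across a range of concentrations.
- The 11% figure extends a line through two points from a different endpoint and challenge, and the day 57 value was not nominally significant.
- Arms are blinded, so timing should be similar across them. The randomized comparison at visit 9 remains valid; what is imprecise is the day it describes.

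A reader might also infer that any visit 10 from 12 weeks onward counts as day 127. It does not: footnote 1's exclusions apply, and footnote 13 makes the ±7 days flexible. The day 127 skin test also belongs to a separate objective, although Protocol 10.4.3 uses skin-test results for durability of response. The flat phase 1b data give no reason to expect an inflated result.

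All of this stands and limits the size of the problem. It does not remove the overlap of the windows or the lack of any actual-day analysis.

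**Conclusion.** The point holds as a gap in the secondary analyses of duration. Challenges between day 57 and day 99 share one label, the early side is the wider and was opened for an expected group, and nothing planned separates actual from nominal day. Exposure at the early edge is 1.74 to 2.06 times that on day 85, assuming exponential decline at the stated half-lives.

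Whether this biases the day 85 estimate, and by how much, is unknown. In the illustration it ranges from zero (effect flat after day 57) to 6 percentage points (straight-line decline with three quarters tested on day 57). The risk is more plausible for EEU symptoms, where phase 1b showed a decline, than for the skin test, where the concern is mainly that the day 127 label can cover results from about day 85 onward. The day 29 primary endpoint and the testing hierarchy are not affected. The change is worth making but not critical.

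**What to change.** Keep the nominal-visit analysis as planned. In SAP 11.4, 7.2.2 and 14.1, prespecify:

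1. A table of actual study day from dose #1 for visits 8, 9 and 10, by arm.
2. A supportive analysis of the visit 9 EEU endpoints, in the full analysis set and in CS-A. It could be restricted to challenges near the nominal day, for example day 71 or later, the midpoint (57 + 85)/2. Alternatively, it could model the treatment effect against actual days since dose #1.
3. The same for the day 127 skin test, with one consistent cut-off rule; the midpoint rule would give (85 + 127)/2 = 106.
4. A statement that conclusions on duration of efficacy will be drawn with reference to these analyses.

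This is SAP wording only; visit dates are already collected. The restricted analysis will have fewer participants and wider intervals. Actual day also depends on enrollment date, so a trend across days compares different people and should be read as supportive. Moving early results to another nominal day in the main analysis is not needed.

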11.5. Pooling of Categorical Variables for Statistical Analyses

No categorical variables will be pooled in the analyses.

^[2] If a patient has 2 or more timepoints within the same window, the first non-missing value will be used for analysis.

^[3] Records during this period will be used to calculate the average symptom scores in EEU from 2 to 6 hours.

12. TECHNICAL DETAILS PERTAINING TO INTERIM ANALYSIS/(ES)

Not applicable as no formal interim analysis is planned.

14. APPENDIX

14.1. Summary of Statistical Analyses

Efficacy/PD Analysis:

Endpoint	Analysis Populations	Primary Analysis	Statistical Method	Supportive Analysis	Subgroup Analysis	Other Analyses
Primary E	ndpoint					
EEU TNSS (2- 6 hours)	FAS	Mean at day 29 for 3-mAb versus placebo	ANCOVA model with treatment group and stratification factors as fixed effect and the baseline mean TNSS (2 to 6 hours) at visit 2 as a covariate.	Yes, sensitivity and supplemental analysis described in Section 7.2.1.2	Yes, subgroups are listed in Section 7.2 .1.3	Plots
Secondary	Endpoints					
EEU (2-6 hours): TNSS, TOSS, TSS	FAS	Mean, change and percent change from pre-treatment baseline, at days 29*, 57, 85 for each of anti-bet v 1 monoclonal antibodies versus placebo	Same as above	No	No	Numerical comparison between three anti-bet v 1 monoclonal antibodies.
EEU (2-6 hours): TNSS, TOSS, TSS	FAS with subjects allergic to oak	Mean, change and percent change from pre-treatment baseline, at days 36 for each of anti-bet v 1 monoclonal antibodies versus placebo	Same as above	No	No	Comparison between combined active group versus placebo
EEU (2-6 hours): TNSS, TOSS,	FAS - B	Mean for each of anti-bet v 1 monoclonal antibodies versus placebo	Same as above	No	No	No
CSMS, TSS, TNSS, TOSS, DMS	FAS - B	Mean, change and percent change from pre-treatment and pre-season baseline, in BPS, peak BPS for each of anti-bet v 1 monoclonal antibodies versus placebo	Same as above except for the average pollen count during local BPS will also be used as a covariate in the model.	No	No	Analyses using 30 grains/ m³ as the cutoff for defining BPS start and end

Endpoint	Analysis Populations	Primary Analysis	Statistical Method	Supportive Analysis	Subgroup Analysis	Other Analyses
RQLQ(S)	FAS - B	Mean, change and percent change from pre-treatment and pre-season baseline, in BPS, peak BPS for each of anti-bet v 1 monoclonal antibodies versus placebo	Same as above	No	No	No
Titrated SPT MWD AUC	FAS for Day 29, 57, and 85 FAS with visit 10 performed at least 12 weeks after dose #1 for Day 127	Change and percent change from pretreatment baseline, at days 29, 57, 85 and 127 for each of antibet v 1 monoclonal antibodies versus placebo	Same as above	No	No	Plots; Numerical comparison between three anti-Bet v 1 monoclonal antibodies.
Titrated SPT MWD AUC	FAS - B	Change and percent change from pretreatment baseline, end-of-season to EOS for each of anti-bet v 1 monoclonal antibodies versus placebo	Same as above	No	No	Plots; Analyses using FAS with available in-season data irrespective of whether they received dose 2

Note: *except day 29.

Safety Analysis:

Endpoint	Analysis Populations	Statistical Method	Supportive Analysis	Subgroup Analysis	Other Analyses
AEs	SAF	Descriptive statistics	No	No	No
Laboratory Measures	SAF	Descriptive statistics	No	No	No
Vital sign	SAF	Descriptive statistics	No	No	No
Physical examination	SAF	Descriptive statistics	No	No	No

Protocol: R5713-5714-5715-ALG-21111 Amendment 1 Date: May 31, 2023

14.2. Schedule of Events

		PART A									PART B						
	SCRI	EENINC	j	RAND		Οι	ıt-of-Sea	ason							FOLLOW- UP		
Study Procedure	Screening	Birch EEU	Oak EEU	Rand/ Dosing	Tel	Birch EEU	Oak EEU	Birch EEU	Birch EEU	In- Clinic	Dosing	Tel ¹⁵	Birch EEU	Birch EEU	EOS/ ET	Unsc. Visit ³⁸	
Visit (V) Number	V1 ¹	V2 ⁵	V3 ⁶	V4	V5	V6	V7 ⁶	V8 ⁴⁰	V9 ⁴¹	V10 ^{13,41}	V11 ^{12,13}	V12 ¹³	V13 ¹³	V14 ¹³	V15 ¹³		
Appx. Week (wk)		I			wk1	wk4	wk5	wk8	wk12	~wk18	~wk22		~wk27	~wk32	~wk36		
Visit Day (d)	-d70) to -d1		d1	d8	d29	d36	d57	d85	d127	d155	d156	d190	d225	d253		
Visit Window (days)					±3d	±7d	-7d to +14d	±7d	-28d to +14d	±7d	±7d	+1d	±7d	±7d	±7d		
Screening:																	
Inclusion/exclusion	X	X	X	X		X^{19}	X^{19}	X^{19}	X ¹⁹	X^{19}	X^{19}		X^{19}	X^{19}			
Informed consents	X																
Medical and allergy history ³⁴	X																
Demographics	X																
FSH (postmenopausal women only)	X																
Electrocardiogram ²²	X															X	
Height	X																
Weight	X																
Urinalysis	X															X	

				PAI	RT A							PART B						
	SCRI	EENINC	Ĵ	RAND		Out-of-Season								FOLLOW- UP				
Study Procedure	Screening	Birch EEU	Oak EEU	Rand/ Dosing	Tel	Birch EEU	Oak EEU	Birch EEU	Birch EEU	In- Clinic	Dosing	Tel ¹⁵	Birch EEU	Birch EEU	EOS/ ET	Unsc. Visit ³⁸		
Visit (V) Number	V1 ¹	V2 ⁵	V3 ⁶	V4	V5	V6	V7 ⁶	V8 ⁴⁰	V9 ⁴¹	V10 ^{13,41}	V11 ^{12,13}	V12 ¹³	V13 ¹³	V14 ¹³	V15 ¹³			
Appx. Week (wk)		•			wk1	wk4	wk5	wk8	wk12	~wk18	~wk22		~wk27	~wk32	~wk36			
Visit Day (d)	-d70	0 to -d1		d1	d8	d29	d36	d57	d85	d127	d155	d156	d190	d225	d253			
Visit Window (days)					±3d	±7d	-7d to +14d	±7d	-28d to +14d	±7d	±7d	+1d	±7d	±7d	±7d			
Sensitization/ Specia	lty Labs:																	
SPT birch, birch- related and unrelated common allergens ²	X ^{2*,35}					X^4		X^4	X^4	X^4				X ⁴	X ⁴	X ⁴		
Titrated SPT to birch and birch- related allergens ³		X				X^4		X^4	X^4	X ⁴				X ⁴	X ⁴			
Serum allergen- specific IgE (eg, birch and Bet v 1 sIgE, other related/ unrelated allergens)	X			X ³⁹		X		X	X	X			X	X	X	X		
Serum total IgE				X														
Whole blood for basophil activation test ³¹		X				X							X					
Nasal fluid collection ³³		X				X		X					X	X				

				PA	RT A			PART B								
	SCRI	EENINC	ì	RAND		Out-of-Season									FOLLOW- UP	
Study Procedure	Screening	Birch EEU	Oak EEU	Rand/ Dosing	Tel	Birch EEU	Oak EEU	Birch EEU	Birch EEU	In- Clinic	Dosing	Tel ¹⁵	Birch EEU	Birch EEU	EOS/ ET	Unsc. Visit ³⁸
Visit (V) Number	V1 ¹	V2 ⁵	V3 ⁶	V4	V5	V6	V7 ⁶	V8 ⁴⁰	V9 ⁴¹	V10 ^{13,41}	V11 ^{12,13}	V12 ¹³	V13 ¹³	V14 ¹³	V15 ¹³	
Appx. Week (wk)		l			wk1	wk4	wk5	wk8	wk12	~wk18	~wk22		~wk27	~wk32	~wk36	
Visit Day (d)	-d70	0 to -d1		d1	d8	d29	d36	d57	d85	d127	d155	d156	d190	d225	d253	
Visit Window (days)					±3d	±7d	-7d to +14d	±7d	-28d to +14d	±7d	±7d	+1d	±7d	±7d	±7d	
Exploratory research serum and plasma ³²		X		X		X		X	X		X		X	X	X	
Treatment:																
Randomization				X^{10}												
Administer study drug ¹⁶				X							X ^{11,14}					
Dispense rescue medications ²⁷		X	X			X	X	X	X	X	X		X	X		
Efficacy:																
EEU visits: TNSS, TOSS ^{7,8,9}		X ⁵	X			X^7	X^7	X^7	X^7				X^8	X^8		
e-Diary: TNSS, TOSS, and DMS ²⁴			X^{25}									X	7 26			
RQLQ(S) ²⁸		X]	X				
PFASQ ²⁹		X							X							
Outdoor time questionnaire ³⁰		X								X						

				PA	RT A							PAI	RT B			
	SCRI	EENINC	ĵ	RAND		Οι	ut-of-Sea	ason					FOLLOW- UP			
Study Procedure	Screening	Birch EEU	Oak EEU	Rand/ Dosing	Tel	Birch EEU	Oak EEU	Birch EEU	Birch EEU	In- Clinic	Dosing	Tel ¹⁵	Birch EEU	Birch EEU	EOS/ ET	Unsc. Visit ³⁸
Visit (V) Number	$V1^1$	V2 ⁵	V3 ⁶	V4	V5	V6	V7 ⁶	V8 ⁴⁰	V9 ⁴¹	V10 ^{13,41}	V11 ^{12,13}	V12 ¹³	V13 ¹³	V14 ¹³	V15 ¹³	
Appx. Week (wk)		l			wk1	wk4	wk5	wk8	wk12	~wk18	~wk22		~wk27	~wk32	~wk36	
Visit Day (d)	-d70) to -d1		d1	d8	d29	d36	d57	d85	d127	d155	d156	d190	d225	d253	
Visit Window (days)					±3d	±7d	-7d to +14d	±7d	-28d to +14d	±7d	±7d	+1d	±7d	±7d	±7d	
Safety:																
Vital signs ¹⁸	X	X	X	X		X	X	X	X	X	X		X	X	X	X
Physical examination ¹⁷	X	X	X	X		X	X	X	X	X	X		X	X	X	X
Adverse events	X	X	X	X	X	X	X	X	X	X	X	X	X	X	X	X
Concomitant medications	X	X	X	X	X	X	X	X	X	X	X	X	X	X	X	X
Spirometry/PEF ²³	X ^{23*}	X	X	X ^{23*}		X	X	X	X		X		X	X		X
Laboratory Testing ²	0:															
Hematology ³²	X			X		X		X	X	X			X	X		X
Blood chemistry ³²	X			X		X		X	X	X			X	X		X
Pregnancy test (urine) (WOCBP) ²¹		X	X	X		X	X	X	X		X		X	X	X	X
Pregnancy test (serum) (WOCBP) ²¹	X									X						X
Pharmacokinetics an	nd Immuno	genicity	Samp	ling:												
Drug concentration sample ³⁶				X ³⁶		X		X	X	X	X ³⁶		X	X	X	X
ADA sample ³⁶				X ³⁶					X		X ³⁶				X	X

		PART A										PAI	RT B			
	SCRI	EENINC	j	RAND		Out-of-Season								FOLLOW- UP		
Study Procedure	Screening	Birch EEU	Oak EEU	Rand/ Dosing	Tel	Birch EEU	Oak EEU	Birch EEU	Birch EEU	In- Clinic	Dosing	Tel ¹⁵	Birch EEU	Birch EEU	EOS/ ET	Unsc. Visit ³⁸
Visit (V) Number	V1 ¹	V2 ⁵	V3 ⁶	V4	V5	V6	V7 ⁶	V8 ⁴⁰	V9 ⁴¹	V10 ^{13,41}	V11 ^{12,13}	V12 ¹³	V13 ¹³	V14 ¹³	V15 ¹³	
Appx. Week (wk)		•	•		wk1	wk4	wk5	wk8	wk12	~wk18	~wk22		~wk27	~wk32	~wk36	
Visit Day (d)	-d70	0 to -d1		d1	d8	d29	d36	d57	d85	d127	d155	d156	d190	d225	d253	
Visit Window (days)					±3d	±7d	-7d to +14d	±7d	-28d to +14d	±7d	±7d	+1d	±7d	±7d	±7d	
Future Biomedical F	Research (o _l	ptional s	sub-stu	dy):												
Serum sample collection for future biomedical research (optional) ³²		X		X		X		X	X		X		X	X	X	
Plasma sample collection for future biomedical research (optional) ³²		X		X		X		X	X		X		X	X	X	
Pharmacogenomics ((optional sub-study):															
Blood for DNA (optional) ³⁷				X												

Footnotes for the Schedule of Events Table

- 1. Screening visit 1 can be split into additional visits, if required, to ensure medication washouts prior to any assessments being performed (per PI discretion).
- 2. Screening skin prick test (SPT) for birch and for other birch-related (eg, alder, oak) and unrelated common allergens (eg, grass, dust mites, etc) is performed as described in the study reference manual. SPT source documentation is required (eg, tape transfer method).
 - * If screening SPT for birch does not meet eligibility at screening visit 1 (mean wheal diameter less than at least 5 mm greater than the negative control), then other screening visit 1 procedures may not be performed, as the subject will have failed screening based upon birch skin prick testing (eg, recommend performing birch skin prick testing prior to blood draw, spirometry, etc).
- 3. Titrated SPT with serial allergen titration for birch and related allergens is performed as described in the study reference manual. The titrated SPT should be performed prior to the EEU challenge during visits when both are scheduled.
- 4. Post-randomization SPT and titrated SPT will be performed in a blinded fashion (as described in the study reference manual).
- 5. All other eligibility criteria need to be met prior to the screening birch allergen EEU challenge (visit 2). It is recommended that the screening birch challenge is scheduled outside of relevant pollen seasons when pollen-allergic subjects are not significantly symptomatic due to other pollens.
- 6. It is recommended that EEU challenges (including birch and oak EEU sessions) be separated by approximately 1 week or longer between the challenges for a subject to avoid potential impact of any residual symptoms on the assessments, per PI judgement. Similarly, approximately 1 week or longer is recommended between EEU challenges and dosing to avoid any overlap of symptoms, per PI judgement. Eligible subjects who are oak-sensitized will also complete the oak EEU challenge at screening. Oak allergy status for stratification and day 36 challenges will be determined similar to birch EEU criteria during the screening oak challenges.
- 7. Part A EEU challenges: TNSS and TOSS are recorded using an e-diary at baseline and then every ~20 minutes while in the EEU, then continued ~ every 2 hours until ~24 hours after the start of the EEU exposure (except during sleep). After completion of the EEU challenges, use of allergy medicines will be recorded in the e-diary until ~24 hours after the start of the EEU challenges. An assessment of TNSS is performed once prior to the start of the EEU exposure at visits 2, 3, 6, 7, 8, 9. If TNSS ≤2, then the visit activities can proceed. If TNSS is >2, then the visit can be rescheduled within the window. Washouts for medications prior to EEU visits are specified in prohibited medications (Protocol Section 7.9.1).
- 8. Part B EEU challenges: There are no TNSS thresholds for the peak birch pollen season EEU visit (visit 13). The birch EEU challenge at the end of the season (visit 14) may not be performed in grass-allergic participants who are highly symptomatic or unable to wash out allergy relieving rescue medications due to grass pollen allergy symptoms, per PI discretion.

- 9. On a case-by-case basis, an EEU challenge visit window post-randomization may be extended up to +14 days for any illnesses (eg, respiratory illness, common cold, etc) that may potentially confound the assessments and/or potentially impact participant safety, per PI discretion in consultation with the sponsor.
- 10. Randomization may occur within 1 day prior to study drug administration.
- 11. In Part B, participants who received either 3-mAb, 2-mAb, 1-mAb, or placebo in Part A will continue the same treatment in Part B.
- 12. Dosing window for visit 11 is within approximately 0 to 3 weeks prior to start of the anticipated BPS.
- 13. Visit timeframes in Part B (visits 10 to 15) may vary based on the timing and duration of the anticipated BPS. End-of-season EEU challenge (visit 14) should occur after the end of the protocol-defined end of the BPS.
- 14. Dose #2 should be administered at minimum 12 weeks after dose #1.
- 15. Participants will be contacted within 1 day (visit 12) after dose 2 (visit 11) via telephone to monitor safety trends.
- 16. All safety assessments performed at screening must be normal and checked against the inclusion/exclusion criteria prior to study drug administration at visit 4. Similarly, it is recommended to review relevant safety assessments prior to dosing at visit 11. Participants will be observed for 2 hours after receiving the SC dose of study drug. Safety labs may be repeated if any concerns, per PI discretion.
- 17. A full physical exam must be done at screening, visits 4, 11, and 15. A limited relevant physical exam will be done at the remaining visits, per PI judgement, depending on presentation of the participant. Additional relevant physical exams may be conducted during and after completion of the EEU challenges, per PI discretion.
- 18. Vital signs include systolic and diastolic blood pressure, respiratory rate, heart rate, and temperature. Vital signs will be collected in a seated position.
 - *On visit 4 (day 1) and visit 11, vital signs are taken prior to study drug administration and at 2 hours (approximately ±15 min) after completion of study drug administration.
 - Additional vital signs may be recorded during and after completion of the EEU challenges, per PI discretion.
- 19. Inclusion/ exclusion criteria will be verified only to document any changes, not to determine study eligibility.
- 20. Testing for COVID-19 or other respiratory infections may be performed at visits, per site local protocols.

21. If the urine pregnancy test is positive, the site must perform a serum pregnancy test for confirmation. For visit 4 (randomization) if a serum pregnancy test must be performed, study drug cannot be administered unless the serum pregnancy test is negative. For all EEU visits (visits 2, 3, 6, 7, 8, 9, 13, and 14) and early termination, if a pregnancy test must be performed, EEU and associated procedures cannot be performed unless the pregnancy test is negative. Urine pregnancy test can be performed on day -1 of EEU visits and early termination, at the investigator's discretion.

- 22. Electrocardiogram will be performed locally by the site.
- 23. Spirometry will be performed locally by the site. *Spirometry at screening and randomization is required for all participants for eligibility. At other visits, spirometry and/or peak expiratory flow (PEF) may be performed for participants, per PI judgement.
- 24. Daily TNSS, TOSS, and DMS assessments will being collected by e-diary during screening and in Part B from visit 10 to visit 15. The e-diary is returned at visit 15.
- 25. Screening baseline assessment: e-diary assessments for symptoms and allergy rescue medication use should be obtained for an approximate 2-week period or longer (at minimum 1 week) starting after the screening birch EEU challenge until randomization (visit 4) in eligible subjects. It is recommended that it is performed outside of relevant pollen seasons when pollen-allergic subjects are not significantly symptomatic due to other pollens.
- 26. Pre-season baseline assessment: e-diary assessments for symptoms and allergy rescue medication use should be obtained approximately 2 weeks or longer up (at minimum 1 week) to receipt of dose 2 given ahead of the anticipated BPS (starting at visit 10 [Part B]) and prior to receiving dose 2 at visit 11 ahead of the BPS).
- 27. Allergy relieving rescue medications, as needed, should be dispensed at the end of symptom score collection on visits 2, 3, 6, 7, 8, and 9. Rescue medications are dispensed starting at visit 10 for management of symptoms during the pollen season up to visit 15.
- 28. RQLQ(S) is administered weekly starting at visit 2 (during screening baseline assessment period) and then weekly using an e-diary in Part B starting at visit 10 until visit 15.
- 29. Pollen food allergy questionnaire (PFASQ) is administered every 2 weeks at baseline starting at visit 2 (during screening baseline assessment period) and then every 2 weeks in Part B starting at visit 10 until visit 15.
- 30. Outdoor time questionnaire is administered daily at baseline starting at visit 2 (during screening baseline assessment period) and then daily using an e-diary in Part B starting at visit 10 until visit 15.
- 31. Basophil activation test (BAT) samples may be collected from approximately 100 randomized participants (subset of the total enrolled population at one or both EEU sites; additional samples may be collected at the screening EEU visit to account for potential screen failures). The initial samples for a BAT assay are to be collected prior to the administration of study drug and subsequent BAT assay samples are to be collected prior to the respective EEU challenges.
- 32. Samples are to be collected prior to the administration of study drug and prior to EEU challenges, when applicable.

33. Nasal fluid samples may be collected from a subset of participants. It is recommended to collect these samples in the same participants from whom BAT assay samples were collected. It will be collected in approximately 100 randomized participants at visits 2, 6, 8, 13, and 14 (subset of the total enrolled population at one or both EEU sites; additional samples may be collected at the screening EEU visit to account for potential screen failures). At each visit, the nasal fluid samples will be collected at 2 time points, prior to the start of the EEU challenge and then at 6 hours after completion of the challenge.

- 34. Medical, surgical, allergy and medication history, demographic and social history may be obtained from historical data for participants who have available source documentation of these within 6 months prior to screening. At screening, all historical data should be reviewed/confirmed for accuracy and completeness with addition of any other relevant missing and/or interval changes since that last historical assessment. Eligibility criteria must be reviewed during screening to ensure that all inclusion criteria are met, and no exclusion criteria are met.
- 35. Skin prick testing data for allergens using standard diagnostic concentrations of allergen extracts [except birch, other trees (birch-related or unrelated), or grasses] may be obtained from historical data for participants who have source documentation of prior SPT performed within 6 months prior to screening.
